## **Objectives of the study**

### **Research hypothesis:**

The null hypothesis ( $H_0$ ) of this research is that there's no difference between both frictionless and friction mechanics on anchorage loss during “En-masse retraction” following 1st premolar extraction

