## **F] Sample size calculation:**

Our sample size calculation is based on a previous study comparing the effect of friction and frictionless mechanics. Using PS software output, we are planning a study of a continuous response variable from independent Group I and Group II subjects with 1 Group I(s) per Group II subject. In a previous study the response within each subject group was normally distributed with standard deviation 0.76. If the true difference in the Group II and Group I means is 1.0, we will need to study 10 Group II subjects and 10 Group I subjects to be able to reject the null hypothesis that the population means of the Group II and Group I are equal with probability (power) 0.8. The Type I error probability associated with this test of this null hypothesis is 0.05. Considering drop out a sample size 15 per group is appropriate.

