## **C] Statistical Analysis:**

- The principle investigator will be responsible for the extraction of the required data from the CBCT taken before and after retraction as well as the study models taken at every follow up visit. The data will be sent to a specialized statistician.
- The specialized statistician will be responsible for the statistical analysis of the study by:
  1. Presenting the data as mean, standard deviation (SD) and Standard error (SE) values.
  2. Using Paired t-test to compare between the friction and the frictionless group of retraction as well as to compare between the pre-and post -treatment data for each group.
  3. Using Anova test to determine the rate of anterior segment retraction.
  4. Statistically evaluate the patient acceptance for both techniques.
- For this study, the specialized statistician will use IBM11 SPSS12 Statistics Version 20 for Windows to perform the required statistics.
- The significance level will be  $P \leq 0.05$ . Highly significant variables are detected when P value is less than 0.01.

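### Within-arm pre/post significance tests stand on the same footing as the between-arm test, although the trial's question lies only between the arms

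*Protocol*

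**What the plan says.** In the Protocol, section III) C] Statistical Analysis, item 2 puts two comparisons in one sentence. The first is between arms: "Using Paired t-test to compare between the friction and the frictionless group of retraction". The second is within arms: "as well as to compare between the pre-and post -treatment data for each group". Both use a paired t-test and both fall under the section's 0.05 significance level, with a further label for small P values: "Highly significant variables are detected when P value is less than 0.01". Nothing ranks the two comparisons or marks the within-arm one as descriptive. Item 1 gives the summary format: "Presenting the data as mean, standard deviation (SD) and Standard error (SE) values".

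The rest of the Protocol asks a between-arm question:

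- The Research hypothesis section states a null of "no difference between both frictionless and friction mechanics on anchorage loss".
- The Study design section describes two parallel arms, allocated 1:1, whose anchorage loss is to be compared.
- Section I) F] Sample size calculation treats the groups as independent and is built on a between-group difference: "If the true difference in the Group II and Group I means is 1.0".
- Section I) D] Outcomes defines every outcome as a change from T0 to T1.

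**The concern.** Because outcomes are defined as T0 to T1 change, a pre/post test inside one arm tests the primary outcome one arm at a time. It asks whether the molars moved in that arm, which is not the stated null hypothesis. With two such P values printed beside the between-arm one, and no stated order among them, it is easy to write that one technique lost anchorage significantly and the other did not, and to take this as evidence that the techniques differ. That inference does not have the error rate of the randomised comparison.

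The risk depends on how large the change is, and the documents give no expected anchorage loss. Both arms use miniscrew anchorage and eligible cases need maximum anchorage, so a small mean loss is plausible. A small but non-zero loss is where within-arm verdicts disagree most by chance. Item 2 is not limited to one outcome, so the same issue arises for the other continuous pre/post outcomes.

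**Working it through.** **Inputs.** All from section I) F] Sample size calculation:

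- SD: "the response within each subject group was normally distributed with standard deviation 0.76".
- Difference in means 1.0, power 0.8, and 10 per arm, raised to 15 for dropout.
- Alpha: "The Type I error probability associated with this test of this null hypothesis is 0.05". Two-sided testing is assumed, since the section does not say.

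Two further assumptions: 0.76 is the SD of T0 to T1 change, and the unit is mm. The section states neither.

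**The plan's own figure.** n = 2 × (1.960 + 0.842)² × 0.76² / 1.0² = 9.07, rounded up to 10 per arm. This reproduces. Power from the noncentral t distribution is 0.795 at 10 per arm and 0.935 at 15.

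**Disagreement between two identical arms.** Let p be the power of the within-arm test (one-sample t on change, noncentrality = mean change / (0.76/√n), two-sided 0.05). The arms are independent, so exactly one is significant with probability 2p(1−p).

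| True change in both arms | p, n=10 | Disagree, n=10 | p, n=15 | Disagree, n=15 |
|---|---|---|---|---|
| 0 | 0.050 | 9.5% | 0.050 | 9.5% |
| 0.3 | 0.201 | 32.1% | 0.297 | 41.7% |
| 0.4 | 0.319 | 43.4% | 0.475 | 49.9% |
| 0.5 | 0.459 | 49.7% | 0.659 | 44.9% |
| 0.6 | 0.605 | 47.8% | 0.811 | 30.6% |
| 1.0 | 0.958 | 8.1% | 0.997 | 0.6% |
| 1.5 | 1.000 | about 0% | 1.000 | about 0% |

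2p(1−p) cannot exceed 0.50, which it reaches at p = 0.5. That needs a true change of 0.53 at 10 per arm or 0.41 at 15. Simulating 100,000 trials at each peak gave disagreement of 49.7% (n=10) and 50.0% (n=15). A two-sample t-test on the same data was significant in 4.9% and 5.1%.

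**Sensitivity to the SD.** The 50% ceiling does not depend on the SD; only its location does. The peak lies at 0.694 SD (n=10) or 0.543 SD (n=15):

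- SD 0.5: 0.35 and 0.27.
- SD 0.76: 0.53 and 0.41.
- SD 1.0: 0.69 and 0.54.

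**The opposite failure.** Suppose the arms truly change by 1.0 and 2.0, a difference equal to the planning value. At 15 per arm the within-arm powers are 0.997 and about 1, so the verdicts differ in only about 0.3% of trials (1 − 0.997). At 10 per arm it is about 4.2% (1 − 0.958). Agreement between within-arm verdicts therefore says nothing about whether the arms differ.

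**Precision of the direct contrast.** The 95% CI half-width is t(0.975, 2n−2) × 0.76 × √(2/n):

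- n=10: 2.101 × 0.340 = 0.71.
- n=15: 2.048 × 0.278 = 0.57.

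At 15 per arm, an estimated difference of 0.5 would have a CI of −0.07 to 1.07. It would be non-significant, yet compatible with both zero and the planning difference of 1.0.

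**The case against.** The strongest defence is that the between-arm comparison comes first in the very sentence at issue, and that the hypothesis, design and sample size all point to it. A reader might infer from item 2 that the randomised comparison has been set aside, or that half of such trials would declare a false difference. The documents support neither. They nowhere say that conclusions will come from setting one within-arm P value against the other, and the disagreement rates apply only if someone does that.

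A reader might also infer that a null result could not be interpreted because item 1 lists only mean, SD and SE. That does not follow. The format of estimates and intervals is commonly left to a statistical analysis plan, which is not shown here, and item 1 excludes nothing. An interval can be computed from each arm's mean, SD and n, provided these describe the change; SDs at T0 and T1 alone do not give the SD of change. The absence of an interval is therefore not a defect in its own right.

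It is also fair that a paired pre/post test is a valid way to describe whether change occurred in an arm. What remains is that item 2 gives it equal standing as a significance test. The between-arm safeguard is moreover misnamed: a paired t-test has no natural pairs in two independent arms, and it contradicts the independent-groups basis of the sample size.

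**Conclusion.** The point holds as a matter of ranking and wording. Item 2 sets within-arm tests, which do not address the hypothesis, beside the between-arm test at the same threshold and without order. If differing within-arm verdicts were read as a difference, identical arms would disagree in 9.5% of trials at zero change, in at most 50% at about 0.4 to 0.5 mm, and in 0.6% (n=15) to 8% (n=10) at 1.0 mm. The direct two-sample test errs in about 5%. The 50% is a ceiling at one size of change, not an expected rate. The location of the peak rests on 0.76 being the SD of change in mm, and all rates assume two-sided testing at 0.05.

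The 1.0 in the sample size section is an assumed true difference for power. A reader might take it as the smallest clinically important difference, but the Protocol does not call it that.

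**What to change.** Reword item 2 of section III) C] Statistical Analysis along these lines:

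- For each continuous outcome, the between-arm difference in T0 to T1 change, from an independent-samples comparison and with its 95% CI, is the sole basis for conclusions. The paired t-test is no longer named for the comparison across arms.
- Within each arm, mean change with its 95% CI is shown as description only, either without P values or with P values labelled descriptive.
- A non-significant between-arm result is reported with its CI and not as proof of no difference. The 1.0 may be cited as the planning difference, but not as an established clinical margin.

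The first two parts must be changed together. Deleting the within-arm clause alone would leave only the paired test across independent arms.

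The cost is a short rewording and standard SPSS output. Sample size, data collection and patient procedures are unaffected. The downside is the loss or demotion of within-arm P values.

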### **Outcome measure:**

	Outcome Name	Measuring Tool	Measuring Unit
Primary Outcome	Anchorage loss	CBCT	

- Linear measurement in mm

Angular measurement in degrees

Secondary Outcome	Rate of space closure	Digital scanned Dental Model	

- Scanned digital models in (mm)

○ Models taken every month

○ Analysed using 3 Shape Software

	Pain	Pain scoring sheets given to patients	VAS scoring from 1-10 (Fig 1)

	Root resorption	CBCT	Scoring system of Levander and Malmgren[39] (5 grades classification)
	Torque of anterior teeth	CBCT	Degrees
	Tip of anterior teeth	CBCT	Degrees
	Vertical position	Digital scanned Dental Model	Mm
	1 st Permanent Molar rotation	Digital scanned Dental Model	Degrees

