## D] Outcomes

[figure not shown]
**Primary outcome:** is to monitor the anchorage loss during “En-masse retraction”. All outcomes will be assessed as the difference between T0 at the start of retraction and T1 after complete space closure.

**Secondary outcomes:** is to monitor the changes in the anterior teeth position (final anterior teeth tip, torque and vertical position), rate of space closure, presence of any root resorption and pain associated with the different methods used for retraction.

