##### ***Secondary outcomes:***

**1. Retraction rate:** to assess the antero-posterior movement of anterior teeth and first molars, the principle investigator will take study models for every participant monthly during the follow up visits. Then will digitize the models and identify the landmarks, reference lines and planes on the pre, interim and post-retraction digital dental models for measurements reading. Also, by identifying the landmarks, reference lines and planes using CBCT taken before and after the completion of retraction.

**2. Pain:** each patient will fill a questionnaire regarding his treatment experience in a Visual Analog Scale (VAS) scoring from 1-10 by making a handwritten mark on a 10-cm line that represents a continuum between “no pain” on the left end (0 cm) of the scale and the “worst pain” on the right end of the scale (10 cm). The questionnaire will include several questions related to oral hygiene, pain and discomfort experienced throughout the trial.

**3. Root resorption:** will be accessed by the principle investigator via CBCT taken before and after the completion of retraction. The resorption will be identified using

scoring system of Levander and Malmgren that classifies it into 5 grades: 0, no root resorption; 1, mild resorption, with the root of normal length and only an irregular contour; 2, moderate resorption, with small areas of root loss and the apex having an almost straight contour; 3, severe resorption, with loss of almost one third of root length; and 4, extreme resorption, with loss of more than one third of the root length.

**4. *Anterior teeth torque:*** will be accessed by the principle investigator via CBCT taken before and after the completion of retraction. The principal investigator will identify the landmarks, reference lines and planes, then will interpret the measurements in degrees.

**5. *Anterior teeth extrusion/intrusion:*** will be accessed by the principle investigator via CBCT taken before and after the completion of retraction. The principal investigator will identify the landmarks, reference lines and planes, then will interpret the measurements in millimeters.

**6. *Anterior teeth tip:*** will be accessed by the principle investigator via scanned digital models taken before and after the completion of retraction.

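### The secondary rate outcome has two conflicting definitions and two conflicting sets of readings, and the ANOVA named for it neither yields a rate nor allows for repeated readings per patient

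*Protocol*

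**What the plan says.** The outcome table under Aim of the study lists "Rate of space closure" as a secondary outcome, measured on scanned dental models, with the note "Models taken every month". Section D] Outcomes again names the "rate of space closure", and states that every outcome is a change from T0 (start of retraction) to T1 (space fully closed).

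The secondary objective speaks instead of the rate of en-masse retraction. Under III) A] Data collection methods, the item is headed as retraction rate. Its purpose is "to assess the antero-posterior movement of anterior teeth and first molars", and for this the investigator "will take study models for every participant monthly during the follow up visits". The same item adds CBCT before and after retraction as a further source. The retraction records paragraph in C] Interventions bases the rate on the final dental model.

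Under III) C] Statistical Analysis, the data passed on for analysis are the CBCT measurements "as well as the study models taken at every follow up visit". The only method given for this outcome is "Using Anova test to determine the rate of anterior segment retraction". No factors, unit of analysis or between-arm term are given.

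**The concern.** Two things are left open that decide what the result means.

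The first is the quantity. The extraction space closes from both ends: the anterior teeth move back and the molars move forward. Forward molar movement is anchorage loss, which the trial treats as the harm to be limited. A rate of space closure counts it as progress; a rate of anterior retraction does not. The secondary outcome could then favour the arm that does worse on the primary outcome.

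The second is the data and the test. Monthly models give several correlated readings per patient, whereas a T0 to T1 change gives one. An ANOVA named without factors does not say how readings from one patient are handled, and its F-test is not a rate. If it were run on all readings as separate observations, the arm comparison would claim more information than the patients provide.

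**Working it through.** **The Protocol's own figure.** It gives no number for the rate analysis. Its only calculation is in F] Sample size calculation: SD 0.76, difference 1.0, power 0.80, alpha 0.05 (taken as two-sided).

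n per group = 2 × [0.76 × (1.960 + 0.842) / 1.0]² = 9.07, rounded up to 10. This matches the stated 10 per group (t-based power at 10 is 0.795). Nothing below changes it.

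**Definitions and readings side by side.**

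| Place in Protocol | Quantity | Readings |
|---|---|---|
| Outcome table | space closure | monthly models |
| Secondary objective | en-masse retraction | not stated |
| C] Interventions, retraction records | retraction | final model |
| D] Outcomes | space closure | T0 to T1 change |
| III) A] Data collection | retraction; anterior teeth and first molars both tracked | monthly models, plus CBCT before and after |
| III) C] Statistical Analysis | anterior segment retraction | models from every visit |

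**Effect of the definition.** Space closed = anterior retraction + mesial molar movement. Suppose anterior retraction and duration are the same in both arms, and molar movement differs by 1.0 mm. Two assumptions enter: the 1.0 in the sample size section is read as mm of anchorage loss (outcome and unit are not named there), and retraction lasts 4 to 8 months (no duration is given).

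- 4 months: 1.0 / 4 = 0.25 mm per month
- 8 months: 1.0 / 8 = 0.125 mm per month

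That is the apparent difference in closure rate with no difference in anterior retraction. If instead both arms close the same space at the same anterior speed, the arm with more molar movement finishes sooner, so the direction is the same.

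**Effect of pooling monthly readings in an arm comparison.** Let m be the readings per patient and ρ the correlation between any two of them. The Protocol gives neither, so both are assumed. Treating the readings as independent understates the variance of an arm mean by the factor 1 + (m − 1)ρ. The type I error at nominal 0.05 is then about 2 × [1 − Φ(1.96 / √(1 + (m − 1)ρ))]. Simulation of 20,000 null trials per setting, 15 patients per group:

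| m | ρ | 1 + (m − 1)ρ | Formula | Simulated, pooled | Simulated, one mean per patient |
|---|---|---|---|---|---|
| 4 | 0.1 | 1.3 | 0.086 | 0.089 | 0.054 |
| 6 | 0.3 | 2.5 | 0.215 | 0.219 | 0.050 |
| 8 | 0.5 | 4.5 | 0.356 | 0.366 | 0.049 |

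At ρ = 0 the pooled test stays at 0.048 to 0.051. Results with 10 per group are nearly the same.

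**Effect on a comparison of months within one arm.** Here an ordinary ANOVA leaves the between-patient variance in the error term. Simulated type I error (15 patients, m = 4 to 8, 5,000 runs) is 0.013 or less for ρ of 0.3 or more. That error is in the conservative direction.

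**The case against.** The strongest reply is that the analysis section fixes very little. It does not say one-way, does not say rows are pooled, and gives no arm term for the ANOVA. The comparison of friction with frictionless stands in the item before it, as a t-test. A repeated-measures ANOVA fits the words, and model detail is commonly left to an analysis plan. On the basis given in D] Outcomes, or in the retraction records paragraph, each patient contributes one value and the dependence problem disappears. The analysis section also names anterior segment retraction, which excludes molar movement, and data collection already refers to landmarks and reference planes.

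Most of this stands. A reader might infer that the trial's false-positive rate is inflated, or that molar drift is certain to be counted as speed. The documents support neither. The first needs pooled rows and an arm test, which are not prescribed. The second follows only from the space-closure label, for which no formula is given. A reader might also infer that a repeated-measures ANOVA would drop the fastest closers. That would need deletion of incomplete series over a window running past the earliest finishers, and the Protocol sets neither.

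The reply does not remove the contradictions. An analysis plan can choose a model, but here the Protocol itself names two different quantities and two different sets of readings for one outcome. The one method it names does not settle either choice.

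**Conclusion.** The point holds as a conflict of definition and of data source, joined to a named test that does not fit the outcome. A space-closure rate would credit the arm with more anchorage loss, by 0.125 to 0.25 mm per month under the assumed 4 to 8 months and the reading of 1.0 as mm of anchorage loss. The type I error of about 9% to 36% is conditional: it applies only if monthly readings are pooled as independent in an arm comparison, with 4 to 8 readings and correlation 0.1 to 0.5, all assumed. Other readings of the text give about 5%, or a conservative test. The matter concerns one secondary outcome and should be corrected, but it does not touch the primary conclusion.

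**What to change.** 1. In the outcome table, D] Outcomes, III) A] Data collection and III) C] Statistical Analysis, use one definition: displacement of the anterior segment against a named, stable reference plane, divided by the time actually elapsed. Report molar movement separately.
2. State which readings enter the rate, and bring D] Outcomes and the retraction records paragraph into line with the monthly models.
3. Replace the ANOVA with a between-arm comparison of one rate (slope) per patient by an independent-samples test, since the arms are parallel. Alternatively, fit a linear mixed model with arm, time, arm-by-time and patient random effects; the arm-by-time term is then the difference in rate. The mixed model also uses series of unequal length.

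The cost is wording, including the name of a listed secondary outcome, so it should go through the Protocol's own amendment procedure. Visits, models, scans and patient numbers do not change.

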### **Assessors Reliability:**

- To achieve high reliability for measurements, the supervisor will choose a well-experienced inter-examiner during the study.
- A training session will be provided for the examiners to ensure standard measurements techniques.
- Each examiner will complete the measurements on a model and will repeat the procedure after one week to assess the intra- and inter-examiner reliability.
- The supervisor will compare the measurements of the two assessors for disagreement with a difference of more than one millimeter.
- the supervisor will evaluate the amount of variation in measurements among and between examiners to test the performance of each assessor.
- The examiner with less reliability will receive additional training but will be replaced during the study.
- The specialized statistician will calibrate the intra and inter-examiner reliability for the measurements of the study by the Intra-class correlation coefficient (ICC). The closer the ICC to 1.0, the higher reliability between assessors. According to Fleiss:" ICC values between 0.7 and 0.9 represent good reliability.". The kappa scores between study examiners will be calculated, a range of 0.60-0.80 will represent acceptable reliability.

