***Friction group:***

- Crimpable hooks added to the arch wire (0.017"x0.025" Stainless steel) distal to the lateral incisor passing near the center of resistance of the anterior segment.
- A ligature wire extending between the second premolar and miniscrews will be used for proper anchorage control.
- Retraction will start on a 0.017"x0.025" Stainless steel wire using elastomeric chain (force applied will be 200 g per side) [43] extending between the crimpable hooks and the miniscrews.
- The force will be measured by a force gauge and reactivated every 4 weeks maintaining constant force of retraction all over the retraction phase.

➢ **Follow up visits**

Patients will be asked to attend for follow up sessions every 4 weeks for:

- Evaluation miniscrews stability.
- Replacement of the power chain to maintain a force of 200 gm per side.
- Reactivation of the T-loop by further distal activation and cinch back.
- Impression taking to determine the anchorage loss

➤ **Criteria for discontinuing or modifying the allocated intervention:**

In cases of prolonged swelling or pain related to the miniscrews, the patient will be given strict oral hygiene measures and may wait for three weeks before the beginning of retraction.

In cases of loose or broken miniscrews, the screw will be removed and replace the miniscrew after total resolution of the inflammation.

➤ **Criteria for Ending the retraction:**

a-class I canines

b-normal overjet

c- closure of extraction space

d- reaching good profile

Ø **Post-retraction Questionnaire:**

The patients of both groups will be asked to fill in questionnaires regarding their experience with their allocated technique during the whole retraction period from day of extraction till the end of retraction.

Ø **Retraction records**

Following “En-masse retraction”, patients will be referred to the same radiology center to acquire the final cone-beam CT to assess the movement and inclination of anterior teeth.

The final dental model will be used to assess the rate of retraction and molar anchorage loss achieved throughout the study.

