### **III) Data collection, management and analysis:**

#### **A] Data collection methods:**

##### ***Primary outcomes:***

**1. Anchorage loss:** will be accessed by the principal investigator via CBCT taken before and after the completion of retraction by identifying the landmarks, reference lines and planes, then will interpret the measurements in degrees and millimeters.

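### The protocol gives the CBCT reading of the primary outcome both to two blinded assessors and to the principal investigator, and describes its repeat reading for models only

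*Protocol*

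**What the plan says.** All places are in the protocol.

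- **Outcome measure (table)** puts the primary outcome, anchorage loss, on CBCT, as a linear measurement in mm and as "Angular measurement in degrees".
- **Blinding** calls the study single blinded, with only the outcome assessors blind. Patients' names are hidden on radiographs and models, and two assessors then measure independently. Operators cannot be blinded.
- **Data collection methods, Primary outcomes** says that anchorage loss "will be accessed by the principal investigator via CBCT taken before and after the completion of retraction by identifying the landmarks". The Secondary outcomes list names the principal investigator again for every image- or model-based outcome.
- **Statistical Analysis** makes the principal investigator responsible for extracting the CBCT and model data that go to the statistician.
- **Participant timeline** has the principal investigator allocate patients and take the T0 and T1 records. The retraction-rate item adds the monthly study models.
- **Assessors Reliability** describes the repeat: "Each examiner will complete the measurements on a model and will repeat the procedure after one week to assess the intra- and inter-examiner reliability". It also plans ICC and kappa, and says of the weaker examiner: "The examiner with less reliability will receive additional training but will be replaced during the study".
- **Retraction records** also uses models for part of the picture: "The final dental model will be used to assess the rate of retraction and molar anchorage loss achieved throughout the study".

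**The concern.** Placing landmarks on a CBCT involves judgement. A reader who knows which mechanics a patient received can shift the measured anchorage loss in one direction without meaning to. Such a shift adds directly to the difference between groups, and a larger sample does not reduce it. Assessor blinding is the only protection the protocol offers, because patients and operators are not blinded. If the principal investigator's reading is what gets analysed, that protection does not reach the primary outcome.

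The reliability section should show that the primary measurement is reproducible. Its one described repeat uses a different type of record, and its rule for an unreliable examiner cannot be carried out as worded.

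**Working it through.** **1. The plan's own figure.** Sample size calculation gives SD 0.76, difference 1.0 (no unit), power 0.8 and alpha 0.05. Taking the test as two-sided, n per group = 2 × (1.960 + 0.842)² × 0.76² / 1.0² = 2 × 7.851 × 0.5776 = 9.07, rounded up to 10. The exact t-test solution is 10.12, with power 0.795 at 10 per group and 0.935 at 15. The stated 10 is reproduced, and nothing below changes it.

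**2. Who reads the CBCT?**

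| Section | Reader | Blinded? |
|---|---|---|
| Blinding | two assessors | yes |
| Data collection methods | principal investigator, who places landmarks and interprets the values | not stated |
| Statistical Analysis | principal investigator, who extracts the data | not stated |
| Participant timeline; retraction-rate item | principal investigator allocates and takes T0, T1 and monthly records | knows the patient and the group |

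**3. Can these be reconciled?**

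- *The principal investigator is one of the two assessors.* No section says so. It would also fit badly with the blinding: this person allocates, takes the records and continues the treatment, so hiding a name on a scan is weak masking among 15 patients per group.
- *The principal investigator only organises the readings.* This could fit the word extraction in Statistical Analysis. It does not fit Data collection methods, which gives that person the landmark work itself.
- *Both read.* Then no section says whose values are analysed.

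None of these removes the conflict without a change of text.

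**4. How far it reaches.** Data collection methods lists eight outcomes: anchorage loss, retraction rate, pain, root resorption, torque, extrusion/intrusion, tip and molar rotation. Pain is reported by the patient. The other seven name the principal investigator.

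**5. What the repeat covers.** Elsewhere the protocol uses model for the dental cast or its digital scan, as distinct from CBCT (Outcome measure table, Interventions, Statistical Analysis). Inter-examiner ICC on CBCT can be computed from the two assessors' readings under Blinding. Intra-examiner ICC needs a second reading by the same person, and none is described for CBCT.

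**6. The replacement sentence.** An examiner cannot be both retrained for the task and replaced in it, and the linking word suggests that a negation may be missing. The point matters because the Outcomes section defines every outcome as T1 minus T0. If a reader with systematic offset a reads T0 and one with offset b reads T1, the measured change contains b − a. This cancels only when the same reader reads both scans.

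**7. Power.** Suppose that 0.76 excludes reading error and the CBCT ICC is 0.9. The observed SD is then 0.76/√0.9 = 0.801, and power at 10 per group is 0.752. If 0.76 already contains reading error, power stays at 0.795. The protocol says neither, and it gives no CBCT ICC.

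**The case against.** The strongest reply is that the plan is sounder than its wording. The ICC sentence refers to the study's measurements in general, with no limit to models. Kappa between examiners is also planned, and the only graded examiner reading is root resorption, scored on CBCT, so two-examiner CBCT reading was probably intended. Models are not irrelevant either, since Retraction records and Follow up visits ("Impression taking to determine the anchorage loss") tie them to anchorage loss. The number of scans to re-read, and the way two readings become one value, are details that a statistical analysis plan commonly fixes, and none is shown here.

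Most of this stands, and it narrows the reliability point to the missing intra-examiner CBCT repeat. The rule for combining two readings is therefore not counted as a defect. The reply does not resolve the conflict over the reader, which is a contradiction in the protocol's own text, and it does not repair the replacement sentence.

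A reader might also infer three stronger things:

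- *The trial is underpowered through reading error.* The figures in step 7 depend on an assumption that the protocol does not make.
- *The 1 mm rule ("The supervisor will compare the measurements of the two assessors for disagreement with a difference of more than one millimeter") tolerates errors as large as the effect sought.* That rule flags disagreement and is not an acceptance limit. Its match with the 1.0 in the sample size also needs a unit that is not given.
- *The repeat must include a particular number of patients.* The text says only that "ICC values between 0.7 and 0.9 represent good reliability" and sets no confidence-limit criterion. With two readings under a one-way model, 12 patients give a lower 95% limit of 0.702 at an observed ICC of 0.9, while 30 give only 0.62 at 0.8. The number depends on the ICC assumed.

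**Conclusion.** The contradiction over who reads the CBCT is established from the text and is the main point. It affects the primary outcome and six secondary outcomes. The documents do not show that the primary outcome will be read unblinded; they show that following Data collection methods and Statistical Analysis as written would allow it. The possible bias in mm cannot be quantified from the protocol, so the case rests on whether the claim of blinded assessment can be supported, and no loss of planned power is part of it.

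Two smaller points are also confirmed: no repeat reading is described that would supply intra-examiner reliability for CBCT, and the sentence on the less reliable examiner cannot be followed. It would be wrong to conclude that CBCT has no reliability check, because the inter-examiner comparison is available. The one assumption is that model means a dental model, as it does elsewhere in the protocol. These points should be corrected before any scans are read.

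**What to change.** - Amend Data collection methods (primary and secondary outcomes) and Statistical Analysis so that the two blinded assessors named under Blinding read the coded CBCTs and models, and their readings are the analysed data. Limit the principal investigator to acquiring and coding records.
- Have the same assessors read T0 and T1 of each patient.
- State in advance which value is analysed. The mean of the two readings is one acceptable option.
- Extend the one-week repeat in Assessors Reliability to a subset of the existing CBCTs, and keep the model repeat for model-based measurements.
- Reword the sentence on the less reliable examiner so that it says either retrained or replaced, and when.

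The cost is protocol wording and some extra reading time on scans already taken, with no new imaging. If the two readings are averaged, pairs that disagree widely still need to be examined, because a mean can hide them.
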